6.3.10. CT/MRI

The trial plans to use data from neuroimaging examinations performed within 48 hours prior to patient inclusion in the trial to assess patient status and eligibility for inclusion/non-inclusion criteria at screening (Visit 0). A repeat CT/MRI scan is not required if these findings are present.

6.3.11. Patient assessment using specialised scales

Conducted according to the trial procedure schedule to assess the patient's condition for subsequent analyses of therapy efficacy using the following scales:

- mRS (Modified Rankin Scale) - score on Visits 0, 2, 4;
- NIHSS (The National Institutes of Health Stroke Scale) - score on Visits 0, 2, 4;
- Montreal Cognitive Assessment Scale MoCA - score on Visits 1, 2, 4;
- Hospital Anxiety and Depression Scale (HADS) - scores on Visits 1, 2, 4;
- Rivermead Mobility Index - score on Visits 1, 2, 4.

6.3.12. Recording of adverse events

Adverse Events (AEs) will be recorded by the Investigator during the course of the trial according to the procedures presented in Section 8.2.

6.4. Restrictions of the trial

The Investigator will explain to the patient that the patient must abide by certain restrictions while participating in the trial. Such restrictions are also detailed in the Patient Information Sheet with Informed Consent Form.

Therapeutic regimen

In the present trial, the patient has the responsibility to comply with all recommendations of the investigating physician for primary and concomitant therapy and lifestyle.

Contraception

Prior to participation in the trial, all patients should be informed about the importance of preventing unwanted pregnancy during participation in the trial and the potential risk factors for unwanted pregnancy. The acceptable contraceptive methods considered in this trial are:

- non-hormonal IUD;
- condom with intravaginal spermicide;
- cervical caps with spermicide;
- diaphragm with spermicide.

A prerequisite for participation in this clinical trial is consent to use the contraceptive methods described above for the duration of the trial or complete abstinence from sexual activity for the duration of the trial.

6.5. Concomitant therapy

Patients will receive standard (baseline) therapy according to the Clinical Guidelines "Ischaemic Stroke and Transient Ischaemic Attack in Adults", 2015.

Baseline therapy includes correction of disorders of systemic and cerebral hemodynamics, rheological and coagulation properties of blood, prevention of complications of stroke. However, standard therapy drugs should not be classified as unauthorized in the present trial.

If concomitant pathology is not a criterion for exclusion of the patient from the trial, the treatment of concomitant pathology within the framework of this protocol is carried out according to the accepted standard scheme. Concomitant therapy drugs should not be classified as unapproved protocols.

Concomitant therapy (other than protocol prohibited drugs) for acute or chronic conditions may be continued as indicated. Information on concomitant medications (trade or international nonproprietary name, dose or dose modifications, indication, start date, discontinuation date) should be recorded in the eCRF.

6.6. Drugs prohibited in the trial

Unapproved or off-protocol drugs include drugs and/or dietary supplements from the following groups:

- A) preparations containing succinic acid and its salts (including reamberin, remaxol, cytoflavin);
- B) preparations containing vitamin B6 and/or its derivatives.
- B) preparations belonging to the groups of antioxidants and antihypoxants (including preparations - 3-hydroxypyridine derivatives: methyl ethylpyridinol, ethylmethylhydroxypyridine succinate (except as used in the investigational therapy)).
- C) drugs with nootropic type of action:
 - citicoline preparations.
 - choline alphoscerate preparations.
 - nootropic drugs of the pyrrolidine series, including piracetam.
 - dimethylaminoethanol derivatives: deanol aceglumate, meclofenoxate.
 - pyridoxine derivatives: pyritinol, pyridoxine+threonine.
 - GABA derivatives and analogues: γ -aminobutyric acid, nicotinoyl-GABA, γ - amino-R-phenylbutyric acid hydrochloride, gopantenic acid, calcium γ -hydroxybutyrate.
 - ginkgo biloba preparations and its derivatives.

- neuropeptides and their analogues with nootropic action.
- 2-mercanthobenzimidazole derivatives: ethylthiobenzimidazole.
- polypeptides and organic composites: cattle cerebral cortex polypeptides, cerebrolysin.
- correctors of cerebral circulation disorders - vinpocetine, xanthinol nicotinate, vincamine, naphthidrofuryl, cinnarizine; combined preparation hexobendine+etamivan+etofylline.
- general tonic agents and adaptogens of plant origin.
- preparations containing acetylaminoanthartaric acid.

7. psychostimulants - salbutiamine. EFFICACY EVALUATION

7.1. Efficacy parameters under trial

According to the purpose and objectives of the present trial, the efficacy of the investigational product vs. comparator product will be assessed by the following parameters:

Primary efficacy criterion:

- The magnitude of change in the patient's **mRS** (Modified Rankin Scale) score at the end of therapy vs. baseline (in points).

Secondary efficacy criteria:

- The magnitude of change in the patient's **mRS** (Modified Rankin Scale) score at the end of parenteral therapy vs. baseline (in points).
- Proportion of disabled patients (**mRS** score 3 or more) at the end of therapy;
- Proportion of disabled patients (**mRS** score 3 or more) at the end of parenteral therapy;
- Proportion of patients with mRS score 0-1 at the end of therapy;
- Proportion of patients with mRS score 0-1 at the end of parenteral therapy;
- The magnitude of change in the patient's **NIHSS** (National Institutes of Health Stroke Scale) score at the end of therapy vs. baseline (in points).
- The magnitude of change in the patient's **NIHSS** (National Institutes of Health Stroke Scale) score at the end of parenteral therapy vs. baseline (in points).
- The magnitude of change in the patient's **MoCA** cognitive status score at the end of therapy vs. baseline (in points).
- The magnitude of change in the patient's **MoCA** cognitive status score at the end of parenteral therapy vs. baseline (in points).
- The magnitude of change in the patient's **Rivermead** Mobility Index score at the end of therapy vs. baseline (in points).
- The magnitude of change in the results of the patient's state assessment by the **Rivermead** mobility index at the end of the parenteral course of therapy vs. baseline (in points).
- The magnitude of change in the patient's **HADS** score at the end of therapy vs. baseline (in points).
- The magnitude of change in the patient's **HADS** score at the end of parenteral therapy vs. baseline (in points).

7.2. Methods for estimating, recording and analysing efficacy parameters

The efficacy of the trial therapy will be assessed using a number of scales and questionnaires at Visits 0, 1, 2, 4 of the trial according to the trial procedures schedule and visit descriptions.

8. Safety and tolerability assessment

8.1. List of safety and tolerability parameters

Safety and tolerability will be assessed throughout the trial (from first use of the investigational product/placebo) using the following data:

- AE/SAE reports data,

- Physical examination data, vital signs (BP, HR, respiratory rate, body temperature),
- Indicators of laboratory analyses and instrumental methods of examination.

A conclusion on the safety of the investigational product will be made after statistical evaluation of all AEs, including serious SAs with at least a possible association with the use of the investigational product.

The Investigator is responsible for notifying the Sponsor of any event that appears unusual, including deviation of a patient's test results from normal values, even if the event may be considered an unanticipated benefit to the patient.

8.2. Methods and timelines for estimating, recording and analysing safety and tolerability parameters

- Physical examination data - assessed at Visits 0, 2, 3, 4.
- Vital signs (BP, HR, RR, body temperature) - assessed at Visits 0, 2, 3, 4.
- Clinical blood test data, blood chemistry, urinalysis - assessed at Visits 0, 2 and 4.
- ECG data - assessed at Visits 0, 2 and 4.
- Frequency and severity of adverse drug reactions (tolerability of therapy) - assessed at all Trial Visits since the first administration of the investigational product/comparator product.

8.3. AE recording and reporting

Adverse events (AEs)

The protocol provides for the recording of all AEs that occur to the patient after the first administration of the trial therapy and until the end of the patient's participation in the trial.

During screening, information about medical adverse events will be attributed to the patient's medical history (pre-existing/concomitant conditions).

The planned trial will record all deviations in the health status of patients (based on the results of physical examination, laboratory and instrumental methods of investigation) from the data obtained at the Screening and from the accepted reference values.

After obtaining the necessary information, the investigating physician will categorise the patient's condition as 'normal', 'clinically insignificant abnormalities' or 'clinically significant abnormalities'. In case the abnormalities detected during the trial have not been previously reported, or there is an aggravation of the patient's condition vs. the data obtained at Screening, the detected abnormalities will be classified as AEs.

If the abnormalities detected during the trial have been recorded at Screening and there is no significant negative trend in the reasonable opinion of the investigator, the detected abnormalities will be classified as clinically insignificant abnormalities (CIA).

All detected abnormalities, irrespective of whether they are attributed to AE or CIA, will be analysed when reporting the results of the clinical trial.

An adverse event is defined as any adverse change in the health status of a patient or subject of a clinical trial/trial to whom a medicinal product has been administered, irrespective of the causal relationship with its use.

An adverse event may be any unfavourable and unintended change (including a deviation of a laboratory indicator from the norm), symptom or disease, the time of occurrence of which does not exclude a causal relationship with the use of the medicinal product, regardless of the presence or absence of a relationship with the use of the medicinal product. The parameters of an AE will be assessed in relation to the variables: severity (non-serious, serious AE), foreseeability (foreseen, unforeseen), severity (mild, moderate, severe, life-threatening, fatal), causality (no/yes; if yes: definite, probable, possible, doubtful, conditional, unclassifiable) and outcome (progression to SAE, stabilisation of condition, recovery without consequences, recovery with consequences, improvement in condition, unknown) as follows:

Serious adverse events (SAEs)

For the purposes of this protocol and in accordance with the legal requirements (National

Standard of the Russian Federation "Good Clinical Practice" GOST R52379-2005 dated 25.09.2005), a serious adverse medical event will be considered to be any adverse medical event that, regardless of the dose of the medicinal product, has resulted in death, is life-threatening, requires hospitalisation or its prolongation hospitalization or its prolongation, has resulted in permanent or significant disability or incapacity for work, is a congenital anomaly or birth defect or other medically significant event.

Severity of AEs

The investigator assesses the severity of an adverse event according to the Common Terminology Criteria for Adverse Events (CTCAE) current version at the time of the trial. If an adverse event cannot be classified according to the CTCAE criteria, the Investigator will select the closest description of the severity of the adverse event from those given in the classification based on personal clinical experience:

Severity	Severity	Definition/Description
1	Mild	No symptoms or mild symptoms, only clinical or diagnostic follow-up is required; no intervention is indicated
2	Moderate	Only minimal, localised or non-invasive interventions are indicated; limitation of daily living activities
3	Severe	Severe or clinically significant but not immediately life-threatening; hospitalization or prolongation of hospitalization indicated; disability; limitation of self-care in activities of daily living
4	Life-threatening/ Disability to work	Life-threatening consequences, urgent intervention required
5	Fatal	Death associated with an adverse event

Determination of the relationship of AE to the investigational product:

The investigator should assess the association of the adverse event with the investigational product:

No - clearly and unequivocally related to extraneous causes only, and does not meet the criteria for an unclassifiable, conditional, doubtful, possible, probable or certain relationship.

Yes - there is a reliable temporal relationship with the use of the investigational product.

Criteria:

- may have been caused by a clinical condition or external factors or other prescribed treatments;
- clear temporal relationship between discontinuation of the investigational product or dose reduction and improvement;
- resumes upon rechallenge;
- is consistent with the known nature of the response to the investigational product.

The degree of certainty of causality with the investigational product will be assessed using the WHO scale, taking into account the trial design (multiple administration):

Definite. Clinical manifestations of AEs, abnormalities of laboratory parameters occur during the period of IP administration, cannot be explained by the presence of existing diseases and the influence of other factors.

Probable. Clinical manifestations of AEs, abnormalities of laboratory parameters are related in time to the use of the investigational product, unlikely to be related to concomitant diseases or other factors.

Possible. Clinical manifestations of AEs, changes in laboratory parameters are related in time to the IP intake, but they can be explained by the presence of concomitant diseases or

taking other drugs and the influence of chemical compounds.

Doubtful. Clinical manifestations of AEs, changes in laboratory parameters occur in the absence of a clear temporal relationship with the use of the investigational product; there are other factors (drugs, diseases, chemicals) that may be the cause of their occurrence.

Conditional. Clinical manifestations of an AE, abnormalities of laboratory parameters attributed to an AE are difficult to assess. Additional data is needed for evaluation, or the data is currently being analysed.

Unclassifiable. Reports of suspected AE cannot be evaluated because there is insufficient information or it is contradictory.

Foreseeability: assessed only for AEs treated as an adverse reaction. An unexpected adverse reaction is an adverse reaction, the nature, severity or outcome of which does not correspond to the information in the current instructions for medical use of the medicinal product or in the investigator's leaflet for an unregistered medicinal product.

Outcome:

The outcome of an AE is assessed as follows:

Transition to the SAE:	AE resulted in a condition that meets the criteria of seriousness (resulted in death, was life-threatening, required hospitalization of the patient or its prolongation, resulted in permanent or pronounced disability or incapacity, congenital anomalies or malformations, required medical intervention to prevent the development of these conditions. In case of any unexpected suspected transmission of an infectious agent through a medicinal product has occurred)
Stabilization of the condition (no change in condition):	AE has not resolved
Recovery with consequences	The resolution of the AE has occurred, but the patient still has some residual effects
Recovery/termination of an AE without consequences:	The AE has completely resolved without observed residual events
Improved condition:	Decrease in the severity of an AE
Unknown:	The outcome of an AE is unknown because the patient did not show up for the follow-up examination and attempts to obtain follow-up information were unsuccessful (lost for follow-up)

Terms used in relation to a medicinal product:

An adverse *reaction* is an unintentional adverse reaction of the body associated with the use of a medicinal product/ investigational product, suggesting at least a possible relationship with the use of the suspected medicinal product/ investigational product.

Unexpected adverse reaction - an adverse reaction, the nature, severity or outcome of which does not correspond to the information in the current instructions for medical use of the medicinal product or in the investigator's leaflet for an unregistered medicinal product.

A serious unexpected adverse reaction (SUAR) is an unexpected adverse reaction that is characterized by features of a SAE.

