Interval (quantitative) data will be described using: arithmetic mean, standard deviation, median, lower (25%) and upper (75%) quartiles, minimum, maximum and coefficient of variation. Categorical (qualitative) data will be described using frequencies, percentages and/or fractions.

To compare quantitative data distributed according to the normal distribution law, it is planned to use standard parametric criteria: Student's t-test for dependent/independent samples, analysis of variance (ANOVA) for repeated measures.

It is planned to use standard nonparametric criteria to compare quantitative data distributed according to a law other than normal: Mann-Whitney U-test, Wilcoxon T-test, Friedman's criterion.

The test for conformity to the normal law of distribution will be carried out using the Shapiro-Wilk test.

Comparisons of frequencies of indicators between treatment groups will be made using Pearson's χ^2 test or Fisher's exact test.

9.7.3. Statistical methods for assessing the safety of using the investigational product and the comparator product

Safety parameters will be analysed in the ITT population.

Safety data will be analysed using the methods outlined for the application of the efficacy data assessment. Analyses of AEs will be performed based on an assessment of the incidence of adverse events / serious adverse events. Adverse events reported during the course of the trial will be presented by frequency (number of patients with AEs and number of such AEs in the group). AEs will also be presented by severity and relationship to investigational product

administration. Comparison of the number of patients with AE between therapy groups will be performed using Fisher's exact test or Pearson's χ^2 test.

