indicator ¹³	Visit 0	Visit 2	Visit 3	Visit 4	Dynamics to Visit 0		Visit 0	Visit 2	Visit 3	Visit 4	Dynamics to Visit 0	
					Abs.	%					Abs.	%
N												
Mean												
Median												
Min												
Max												
Qi												
Q3												
SD												
CV												
Comparison of drugs (statistical test ¹⁴) (p-value)												
Indicator span diagram/ indicator scatter diagram or indicator trend diagram												

Table 11. Safety performance assessment results: repeated measures analysis of variance (template)

Safety Indicator/Investigational Product	SS	DF	MS	F	p
Intercept					
Investigational Product					
Error					
Visit					
Visit*Dru					
Error					

Table 12. Results of safety indicators assessment: non-parametric repeated measures analysis of variance (Friedman test, template)

Investigational Product					
Indicator					
Visit	Average rank	Sum of ranks	Mean	SD	p
Visit 1					
...					

¹³ SBP, DBP, HR, RR, body temperature.

¹⁴ T-test for independent samples or Mann-Whitney test depending on the type of distribution of the indicator

Version 1.0 of 12.11.2021

**Plan for statistical analysis of efficacy and safety parameters***Table 13. Frequency analysis of safety performance outcome assessment (template)*

Investigational Product		Mexitol®			Placebo		
		Visit 0	Visit 2	Visit 4	Visit 0	Visit 2	Visit 4
Indicator 1							
Normal	Abs.						
	%						
Deviation	Abs.						
	%						
	%						
Comparison of groups (statistical criterion ¹⁵)							
p-level							
Indicator 2							
...							

Table 14. Frequency analysis of the safety outcome measure score (clinical significance, template)

Investigational Product		Mexitol®			Placebo		
		Visit 0	Visit 2	Visit 4	Visit 0	Visit 2	Visit 4
Indicator 1							
Deviation is clinically significant	Abs.						
	%						
Deviation is clinically insignificant	Abs.						
	%						
	%						
Comparison of groups (statistical criterion ¹⁶)							
p-level							
Indicator 2							

¹⁵ Pearson's χ^2 criterion or Fisher's exact test¹⁶ Pearson's χ^2 criterion or Fisher's exact test

Plan for statistical analysis of efficacy and safety parameters

Table 15. Statistical analysis of ECG (template)

Investigational Product		Mexidol®			Placebo		
		Visit 0	Visit 2	Visit 4	Visit 0	Visit 2	Visit 4
Normal	Abs.						
	%						
Deviation	Abs.						
	%						
	%						
Comparison of groups (statistical criterion ¹⁷)							
p-level							

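### Protocol 8.3 labels every stable Screening abnormality clinically insignificant, even one rated significant; if that label feeds SAP Table 14, persisting significant findings drop out of its significant row after Visit 0.

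*Protocol*

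**What the plan says.** Protocol 8.3 sets up two classifications of the same findings.

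- **The rating.** Once the information is in, "the investigating physician will categorise the patient's condition as 'normal', 'clinically insignificant abnormalities' or 'clinically significant abnormalities").
- **The AE sort, new or worse findings.** "In case the abnormalities detected during the trial have not been previously reported, or there is an aggravation" against Screening, the finding is an AE. Clinical significance is not mentioned as a condition.
- **The AE sort, stable findings.** If the abnormality was recorded at Screening and the investigator sees no significant negative trend, "the detected abnormalities will be classified as clinically insignificant abnormalities (CIA").

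The section adds: "All detected abnormalities, irrespective of whether they are attributed to AE or CIA, will be analysed". Its AE definition covers unfavourable and unintended changes, "including a deviation of a laboratory indicator from the norm".

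SAP section 10 tabulates clinically significant and non-significant laboratory deviations by visit and therapy group. The template is "Table 14. Frequency analysis of the safety outcome measure score (clinical significance, template"), with columns for Visits 0, 2 and 4 in each arm and a between-group p-level. Table 13 is the companion table of normal against deviation. For AEs, protocol 9.7.3 states: "Comparison of the number of patients with AE between therapy groups will be performed using Fisher's exact test" or Pearson's chi-square test. SAP Table 20 adds the relative risk with its 95% CI.

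**The concern.** The label given to a stable Screening abnormality has the same name as the middle category of the physician's rating. Stable and insignificant are different properties. A laboratory value rated clinically significant at Visit 0 and identical at Visit 2 is not a new AE, but nothing about it has become less important. Read literally, 8.3 calls it insignificant from Visit 2 onward.

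At stake is the meaning of SAP Table 14. If its post-baseline columns hold the label, the significant row can contain only new or worsened findings after Visit 0, while the Visit 0 column holds everything. A reader comparing columns would see significant abnormalities resolving on treatment when they had only persisted. Sites could also resolve the conflict differently, so the variable would mean different things at different sites.

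**Working it through.** **Step 1. The two classifications, side by side.**

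| Finding | Physician's rating at the visit | Result of the AE sort |
|---|---|---|
| Significant at Screening, unchanged | Clinically significant | Clinically insignificant (CIA) |
| Insignificant at Screening, unchanged | Clinically insignificant | Clinically insignificant (CIA) |
| New or worsened, significant | Clinically significant | AE |
| New or worsened, insignificant | Clinically insignificant | AE |

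The first row is the contradiction. Nothing in 8.3 or the SAP says which value is kept for Table 14.

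**Step 2. Size of the effect on Table 14 if the label is used.** The documents give no abnormality rates, so the rates here are assumptions. From the documents: 304 randomised 1:1, hence 152 per arm, all taken as assessed at Visit 2. Let s be the proportion significant at Visit 0, f the fraction of those still significant and unchanged at Visit 2, and w = 2% the newly significant proportion among the rest.

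- True count at Visit 2 = 152 × [s·f + (1 − s)·w]
- Count if stable cases are relabelled = 152 × (1 − s)·w

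For s = 10%, f = 80%: Visit 0 shows 152 × 0.10 = 15.2. The true Visit 2 count is 152 × (0.08 + 0.018) = 14.9. The relabelled count is 152 × 0.018 = 2.7.

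| s | f | Visit 0 | Visit 2, true | Visit 2, relabelled |
|---|---|---|---|---|
| 5% | 80% | 7.6 | 9.0 | 2.9 |
| 10% | 50% | 15.2 | 10.3 | 2.7 |
| 10% | 80% | 15.2 | 14.9 | 2.7 |
| 10% | 100% | 15.2 | 17.9 | 2.7 |
| 20% | 80% | 30.4 | 26.8 | 2.4 |

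The relabelled count does not depend on f. With s = 10%, an arm in which half of the abnormalities persist and an arm in which all persist both show 2.7, although the true counts are 10.3 and 17.9. The table would carry no information on persistence.

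**Step 3. Secondary observation: dilution of the any-AE comparison.** This concerns the absence of a significance condition for new findings. Table 6.1 lists 33 laboratory items (18 blood count, 8 biochemistry, 7 urine), tested after baseline at Visits 2 and 4. Many are correlated, for instance absolute and relative leukocyte counts, so I take 10 effective items. With q the assumed chance of an out-of-range result per test:

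- New flag per item: u = (1 − q)·[1 − (1 − q)²]
- Background: b = 1 − (1 − u)^10
- Observed any-AE rate = 1 − (1 − p)(1 − b)

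The noise-free rates p are set at 21% and 35%. The 21% is the pooled EPICA frequency (32 of 150), borrowed although EPICA's AE rule is not given; the 35% is assumed. Power is two-sided at 5% with n = 152 per arm:

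power = Φ{[|p₁ − p₂| − 1.96·√(2p̄(1 − p̄)/n)] / √([p₁(1 − p₁) + p₂(1 − p₂)]/n)}

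| q | b | Observed rates | Relative risk | Power |
|---|---|---|---|---|
| 0 | 0 | 21.0% vs 35.0% | 1.67 | 78% |
| 0.5% | 9.5% | 28.5% vs 41.2% | 1.45 | 64% |
| 1% | 18.0% | 35.3% vs 46.7% | 1.33 | 53% |
| 2.5% | 38.9% | 51.8% vs 60.3% | 1.17 | 32% |
| 5% | 62.2% | 70.1% vs 75.4% | 1.08 | 18% |

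The outcome is driven by q, on which the documents are silent.

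**The case against.** The strongest reply is that 8.3 assigns the three-way rating and only then sorts findings into AE or CIA, so the sort may serve AE reporting alone. The rows of Tables 13 and 14 match the physician's categories directly. If Table 14 is built from that rating, there is no artefact. This stands, and it is why the point is conditional. It does not remove the contradiction, because the protocol uses one term for both and the SAP does not say which applies.

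A reader might infer that Table 14 will show a false improvement on the active drug. The documents do not support that. The source variable is not stated, the same rule applies in both arms under blinding, and the table's test is between groups. Any artefact is a fall from Visit 0 within each arm. Table 13 and the quantitative laboratory analyses (Tables 9, 11 and 12) do not use the label.

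A reader might also infer that the AE comparison is swamped and a real excess hidden. Dilution is possible but not shown. Backgrounds near 100% need a high flag rate and many independent tests together: with q = 5% and all 33 items independent, b = 1 − (1 − 0.0926)^33 = 96% and power is about 5%. The AE definition also requires an unfavourable change, so harmless deviations need not all count. AEs are further split by severity, relationship, adverse reaction, seriousness and preferred term (Tables 21 to 26 and 31), and SAEs have their own comparison (Table 36). Broad capture followed by grading is a defensible choice.

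**Conclusion.** The relabelling point holds. Protocol 8.3 classifies a stable Screening abnormality as clinically insignificant without excepting one rated significant, in conflict with the rating in the same section. The consequence for Table 14 is conditional on the label being its source. In that case, with 5% to 20% of patients significant at baseline, 80% of those stable and 2% newly significant among the rest, roughly 8 to 30 patients per arm at Visit 0 would appear as 2 to 3 at Visit 2, against true counts of about 9 to 27. Those rates are illustrative. The effect hides persistent abnormalities in both arms and does not by itself favour either.

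The missing significance condition for new findings is a secondary observation only. It can dilute the any-AE comparison in protocol 9.7.3 and SAP Table 20, to a degree the documents do not allow one to fix. Whether to add such a condition is a trade-off against under-reporting, and I do not press it.

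**What to change.** - **Protocol 8.3:** replace the CIA label for stable Screening abnormalities with a separate status, unchanged from baseline and not an AE. State that the investigator rates clinical significance at each visit on its own merits, so a persisting significant finding keeps that rating.
- **SAP section 10 and Table 14:** state that the table uses this visit-specific rating.

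The cost is a sentence or two in the protocol, matching eCRF guidance and one line in the SAP. No new data are needed, and AE reporting of stable findings does not change.

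If the sponsor also considers a significance condition for new laboratory findings, it should weigh less noise in Table 20 against reliance on investigator judgement to decide what is reported. The present fix does not depend on that decision.
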